2.6 Treatment of high risk SMM

In a randomized open-label phase 3 trial ¹⁷, 119 patients with high-risk smoldering myeloma were randomized to treatment or observation. Patients in the treatment group received an induction regimen (lenalidomide at a dose of 25 mg per day on days 1 to 21, plus dexamethasone at a dose of 20 mg per day on days 1 to 4 and days 12 to 15, at 4-week intervals for nine cycles), followed by a maintenance regimen (lenalidomide at a dose of 10 mg per day on days 1 to 21 of each 28-day cycle for 2 years). The primary end point was time to progression to symptomatic disease. Secondary end points were response rate, overall survival, and safety. After a median follow-up of 40 months, the median time to progression was significantly longer in the treatment group than in the observation group (median not reached vs. 21 months; hazard ratio for progression, 0.18; 95% confidence interval [CI], 0.09 to 0.32; P<0.001). The 3-year survival rate was also higher in the treatment group (94% vs. 80%; hazard ratio for death, 0.31; 95% CI, 0.10 to 0.91; P=0.03). A partial response or better was achieved in 79% of patients in the treatment group after the induction phase and in 90% during the maintenance phase. Toxic effects were mainly grade 2 or lower. Early treatment for patients with high-risk smoldering myeloma delays progression to active disease and increases overall survival. (NCT00480363).

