13. STATISTICAL CONSIDERATIONS

13.1 Study Design/Endpoints

The proportion of patients who achieve progression free at 2 years will be compared to the rate published for the high risk SMM. By the Mayo Clinic model for risk factors, the median time to progression for patients with high risk SMM was only 1.9 years. Therefore, we assume that, a 2-years progression-free rate of 50% will not be considered promising and a true progression free rate of 70% or higher will be considered promising. A single-stage design will be employed with 39 eligible patients entered. If 24 or more of the 39 eligible patients are progression free at 2 years (observed rate of 62%), we will conclude that this treatment warrants further study. The probability of concluding that the treatment is effective if the true rate is 50% is 0.10 and is >0.9 if the true rate is 70%. Assuming a dropout rate of 5%, we will accrue 41 patients to the trial in order to have 39 eligible patients. The Type I and II error probabilities have been derived using exact binomial probabilities.

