13.1.2 Analysis of Secondary Endpoints

The objective response rate (partial response or better according to the modified IMWG criteria) and the proportion of patients with a MRD, CR, PR or MR will be reported with 90% exact binomial confidence interval (CI). The exact 90% CI around response rate will be no wider than 28% with 39 eligible patients.

Time to progression (TTP) is defined as the time from protocol therapy initiation until documented progression, censored at date last known progression-free for those who have not progressed.

To estimate the duration of response (time from objective response to disease progression or death, or date last known progression-free and alive for those who have not progressed or died), progression-free survival (time

CONFIDENTIAL

This document is confidential. Do not disclose or use except as authorized.

from protocol therapy initiation to the disease progression or death from any cause, censored at date last known progression free for those who have not progressed or died), and overall survival (time from protocol therapy initiation to death or date last known alive), the Kaplan-Meier method will be used.

It is expected that approximately 20% of the patients will receive cyclophosphamide (CTX) for mobilization and this may influence the PFS. Therefore, in a secondary analysis the 2 year PFS rate will be evaluated among those patients who did not receive CTX. Assuming that among the 39 eligible patients between 5-20% of the patients receive CTX for mobilization, the treatment will be considered promising if the observed response rate is at least 62%. With this rule, there is at least 80% probability of concluding the treatment is effective, when the true rate is 70% and less than 10% if true rate is 50%.

Safety analysis will be conducted using the Safety Population defined as any patient receiving one dose of study treatment. For toxicity reporting, all adverse events and laboratory abnormalities will be graded and analyzed using CTCAE version 4 as appropriate.

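### The cyclophosphamide-free secondary analysis evaluates 2-year PFS, but its decision sentence applies the 62% cut-off to the response rate, a different endpoint

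*Combined protocol and SAP*

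**What the plan says.** Section 13.1.2 expects about 20% of patients to receive CTX for mobilization and notes that this may affect PFS. It therefore plans that "in a secondary analysis the 2 year PFS rate will be evaluated among those patients who did not receive CTX". The decision rule attached to this analysis is that "the treatment will be considered promising if the observed response rate is at least 62" percent. Its size rests on an assumed share of CTX users, 5–20% of the 39 eligible patients. The operating characteristics claimed for it are these: "there is at least 80% probability of concluding the treatment is effective, when the true rate is 70% and less than 10% if true rate" (that last rate being 50%).

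The same section opens with a different endpoint: "The objective response rate (partial response or better according to the modified IMWG criteria"), to be reported with an exact 90% confidence interval. Its next sentence calls that endpoint simply the response rate.

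Section 13.1 holds the primary rule. Its two reference rates are set as follows: "a 2-years progression-free rate of 50% will not be considered promising and a true progression free rate of 70% or higher will be considered promising". The cut-off is given as: "If 24 or more of the 39 eligible patients are progression free at 2 years (observed rate of 62" percent), in which case the treatment is judged to warrant further study.

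**The concern.** The endpoint that is analysed and the endpoint that decides are not the same. The analysis exists because CTX might affect progression, so its verdict should rest on progression. As worded, it rests on objective response.

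Objective response has no decision framework in this plan. It is estimated with a confidence interval, and no uninteresting or target rate is given for it. The 62%, 50% and 70% have a stated basis only as 2-year progression-free rates, the 50% being tied in Section 13.1 to a median time to progression of 1.9 years.

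At stake is a secondary verdict of promising that could be reached without looking at progression. An ambiguous deciding endpoint also leaves room to choose between two readings once the data are known.

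**Working it through.** **Inputs.** 39 eligible patients, 5–20% receiving CTX, cut-off 62%, rates 50% and 70% (Sections 13.1 and 13.1.2). Partial response or better on lenalidomide–dexamethasone: 79% after induction and 90% during maintenance (Section 2.6). In the same cited trial, the median time to progression under observation was 21 months and the hazard ratio 0.18 (95% CI 0.09–0.32).

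**Step 1: reproduce the primary rule.** With X ~ Binomial(39, p), P(X ≥ 24) is 0.0998 at p = 0.50 and 0.906 at p = 0.70. The plan states 0.10 and above 0.9, so it reproduces. The observed rate is 24/39 = 61.5%, written as 62%.

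**Step 2: size of the CTX-free group.** 39 × 0.80 = 31.2 and 39 × 0.95 = 37.05, so n = 31 to 37.

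**Step 3: which endpoint do the stated error rates fit?** Take r as the smallest integer of at least 0.62n and compute P(X ≥ r).

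| n | r | true rate 50% | 65% | 70% | 75% | 79% |
|---|---|---|---|---|---|---|
| 31 | 20 | 0.075 | 0.603 | 0.808 | 0.936 | 0.981 |
| 32 | 20 | 0.108 | 0.690 | 0.867 | 0.962 | 0.991 |
| 33 | 21 | 0.081 | 0.641 | 0.839 | 0.952 | 0.988 |
| 34 | 22 | 0.061 | 0.592 | 0.807 | 0.939 | 0.984 |
| 35 | 22 | 0.088 | 0.676 | 0.865 | 0.964 | 0.992 |
| 36 | 23 | 0.066 | 0.629 | 0.837 | 0.954 | 0.989 |
| 37 | 23 | 0.094 | 0.707 | 0.887 | 0.973 | 0.995 |

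Under the progression-free reading (50% against 70%), power is at least 0.807 throughout. Type I error is below 0.10 except at n = 32, where 20/32 gives 0.108. The plan's statement therefore fits that reading with one exception.

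Raising the cut-off to 21/32 brings the type I error to 0.055, but power falls to 0.772, so at n = 32 no integer cut-off meets both stated bounds. If 21/34 = 61.8% is counted as 62%, n = 34 gives 0.115 instead of 0.061.

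**Step 4: the rule read literally.** The last four columns also give the chance of passing if the true objective response rate is 65%, 70%, 75% or 79%: 0.59–0.71, 0.81–0.89, 0.94–0.97 and 0.98–0.99. At 90% it exceeds 0.999. As a stress case, let the response rate be 79% and let all 8 CTX recipients be responders who are removed. Passing then needs 28 responders among all 39, and P(X ≥ 28) = 0.90.

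**Step 5: would the corrected rule behave differently on lenalidomide–dexamethasone alone?** Assume exponential progression, so the proportion progression free at 24 months is exp(−(ln 2/21) × 24 × HR). This gives 0.867 at HR 0.18, 0.931 at 0.09 and 0.776 at 0.32. For n = 31 to 37 the chance of reaching r is above 0.999 at 0.867 and 0.970–0.990 at 0.776.

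**The case against.** The strongest reply is that context settles the meaning. The paragraph names PFS as the reason and 2-year PFS as the quantity evaluated, then uses the three percentages of the progression-free rule. Objective response is only to be estimated, so a statistician would be unlikely to apply the cut-off to it. This stands as evidence of intent, and it is why the slip is best treated as a wording error. It does not remove the need to correct a decision sentence that names a different, defined endpoint.

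A reader might go further and infer that the slip makes the rule almost always say promising because the background drugs alone would pass it. The documents do not support that, for three reasons.

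- The 79% and 90% come from a different regimen: nine induction cycles, another dexamethasone schedule and two years of maintenance. Carrying them over is an assumption.
- Setting about 0.98 (response, at 79%) against 0.06–0.11 (PFS, at 50%) compares two different true states as well as two endpoints, so the gap is not the effect of the wording.
- Step 5 shows that lenalidomide–dexamethasone would also be expected to pass the corrected rule. That weakness comes from the 50% null in Section 13.1 and is a separate issue.

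It is also fair that the primary conclusion rests on 24 of 39 progression free, which is worded correctly.

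**Conclusion.** The mismatch is in the current text and holds whatever the true response rate. The plan analyses 2-year PFS and decides on response, using figures that belong to PFS. It is most likely a wording error, and its effect is confined to a secondary analysis. It should not be read as undermining the primary rule.

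The size of the consequence is conditional. Under the literal reading the chance of passing is 0.98–0.99 at a true response rate of 79%, but 0.81–0.89 at 70% and 0.59–0.71 at 65%. These figures assume n = 31 to 37, independent outcomes and a strict 62% cut-off.

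A smaller defect remains after the wording is corrected: the claim of less than 10% fails at n = 32 (0.108).

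Sections 1.1 and 5.1 record that accrual stopped in September 2017, so the actual CTX-free n may be below 31; the documents do not give it. The mismatch applies at any n, but the stated error rates do not carry over. For example, 13 of 20 gives a type I error of 0.132 at a true rate of 50%.

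**What to change.** In Section 13.1.2, replace the reference to the response rate in the decision sentence with the observed 2-year progression-free rate, and state that objective response is estimated only and has no 62% rule.

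Then make the error statement true in one of two ways:

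- List the integer cut-off for each CTX-free n from 31 to 37: 20, 21, 21, 22, 22, 23, 23. This uses 21/32 to keep type I error below 0.10. Power at n = 32 is then 0.77, so the claim of at least 80% needs that exception.
- Keep the 62% cut-off (20/32 at n = 32), say that it is strict and not rounded, and restate the type I error as about 0.11 or less. Power then stays above 0.80 throughout.

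If the actual CTX-free n is below 31, give the cut-off and its exact error rates for that n. The cost is one phrase and a short table or sentence, with no new data and no new analysis. This does not address whether the 50% null can separate the combination from lenalidomide–dexamethasone alone.

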13.2 Sample Size, Accrual Rate and Study Duration

A total of 41 patients will be enrolled. We expect 1.5 years of active accrual (approximately 2 patients per month) and 3 years of follow-up of patients.

The final analyses of progression-based endpoints, such as estimating the 2-year progression-free rate and estimating the TTP distribution, will be conducted at the end of the study, which will occur after either all subjects have progressed or died or 2-years after the initiation of therapy of the last subject enrolled, whichever occurs first.

13.3 Stratification Factors

There are no stratification factors.

13.4 Interim Monitoring Plan

The study will be monitored by the DFCI Data Safety Monitoring Committee (DSMC). The DSMC will meet at least four times a year and more often if needed (e.g., for safety review). For each meeting, the study will be reviewed for safety and progress toward completion. Copies of the toxicity reports prepared by the DSMC meetings will be distributed to the Principal Investigator. The Principal Investigator will then distribute to sub-investigators. Any DSMC recommendations for changes to the study will be distributed to the Principal Investigator and then circulated to sub- investigators by the Principal Investigator. No interim analysis of the outcome data is planned.

13.5 Stopping Rule for Safety

All participants will be evaluable for treatment-related toxicity from the time of therapy initiation. The serious adverse event (SAE) for this purpose is defined as any grade 4 or higher unexpected, adverse event that is assessed as being related to the study intervention.

The following table provides the probabilities of observing 3 or more SAEs after the 20th patient and before the 40th patient. For example, with 20 participants, there is 0.60 probability of observing 3 or more SAEs if a true

CONFIDENTIAL

This document is confidential. Do not disclose or use except as authorized.

Local Protocol #: 16-242

Version Date: 23 January 2018

rate is 15% and the probability is 0.021 if a true rate is 3%.

True SAE rate	1%	3%	5%	10%	15%	20%	30%
Probability (\geq SAEs)	0.001	0.021	0.075	0.32	0.60	0.79	0.96

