1.1 Study Design

This is a phase II study using the combination of Nivolumab and lenalidomide + low dose dexamethasone in patients with high-risk smoldering multiple myeloma. The trial will include a safety run in of 10 patients. If three of the ten patients experience a serious, unexpected adverse event during their first cycle of therapy, the study will be suspended temporarily until further safety review. If any one of the study medications is permanently discontinued for any reason including toxicity, or FDA mandate, the patient may remain on the study at the discretion of the principal investigator.

** As of September 2017, the trial has been put on partial clinical hold by the Food and Drug Administration: all patients are to discontinue nivolumab indefinitely, and no additional patients will be accrued to the trial. Participants may elect to remain on lenalidomide/dexamethasone or lenalidomide therapy alone for disease control after discussion with the overall PI.

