6.2.7 Immune Mediated Cardiac Toxicity

Cardiac *	Management/Next Dose for Nivolumab
≤ Grade 1	Hold dose pending evaluation and observation.** Evaluate for signs and symptoms of CHF, ischemia, arrhythmia or myositis. Obtain history EKG, CK (for concomitant myositis), CK-MB. Repeat troponin, CK and EKG 2-3 days. If troponin and labs normalize may resume therapy. If labs worsen or symptoms develop then treat as below. Hold pending evaluation
Grade ≥2 with suspected myocarditis	Hold dose.** Admit to hospital. Cardiology consult. Rule out MI and other causes of cardiac disease. Cardiac Monitoring. Cardiac Echo. Consider cardiac MRI and cardiac biopsy. Initiate high dose methylprednisolone. If no improvement within 24 hours, add either infliximab, ATG or tacrolimus. Consult algorithm for more details. Resume therapy if there is a return to baseline and myocarditis is excluded or considered unlikely.
Grade ≥2 with confirmed myocarditis	Off protocol therapy. Admit to CCU (consider transfer to nearest Cardiac Transplant Unit). Treat as above. Consider high dose methylprednisolone Add ATG or tacrolimus if no improvement. Off treatment.

*Including CHF, LV systolic dysfunction, Myocarditis, CPK, and troponin
**Patients with evidence of myositis without myocarditis may be treated according as "other event"
Note: The optimal treatment regimen for immune mediated myocarditis has not been established.
Since this toxicity has caused patient deaths, an aggressive approach is recommended.

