Clarification should be made between a serious AE (SAE) and an AE that is considered severe in intensity (Grade 3 or 4), because the terms serious and severe are NOT synonymous. The general term *severe* is often used to describe the intensity (severity) of a specific event; the event itself, however, may be of relatively minor medical significance (such as a Grade 3 headache). This is NOT the same as the *serious*, which is based on patient/event outcome or action, criteria described above, and is usually associated with events that pose a threat to a patient's life or ability to function. A severe AE (Grade 3 or 4) does not necessarily need to be considered serious. For example, a white blood cell count of 1000/mm³ to less than 2000 is considered Grade 3 (severe) but may not be considered serious. Seriousness (not intensity) serves as a guide for defining regulatory reporting obligations.

Adverse event (AE) monitoring and reporting is a routine part of every clinical trial. The following list of reported and/or potential AEs (Section 7.2) and the characteristics of an observed AE (Section 7.3) will determine whether the event requires expedited reporting **in addition** to routine reporting.

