7.2 Expected Toxicities

- Adverse Events List(s)

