7.2.1.2 Other Immune Mediated Adverse Events

For suspected immune-related adverse reactions, adequate evaluation should be performed to confirm etiology or exclude other causes. Based on the severity of the adverse reaction, nivolumab should be withheld or discontinued, and corticosteroids administered accordingly. Upon improvement, nivolumab may be resumed after corticosteroid taper. If there is recurrence of any Grade 3 or 4 immune-related adverse reactions or life-threatening immune-related adverse reactions, nivolumab must be permanently discontinued. Rare cases of myotoxicity (myositis, myocarditis, and rhabdomyolysis), some with fatal outcome, have been reported with nivolumab. If a patient develops signs and symptoms of myotoxicity, close monitoring should be implemented, and the patient referred to a specialist for assessment and treatment without delay. Based on the severity of myotoxicity, nivolumab should be withheld or discontinued, and appropriate treatment instituted. For Grade 3 myocarditis, nivolumab should be permanently discontinued.

The following events have been identified during post approval use of nivolumab. Because reports are voluntary from a population of unknown size, an estimate of frequency cannot be made.

- Solid organ and tissue transplant rejection has been reported in patients who have previously undergone transplantation and who were subsequently treated with programmed cell death 1/programmed cell death ligand 1 (PD-1/PD-L1) inhibitors, including nivolumab. Treatment with nivolumab may increase the risk of rejection in solid organ or tissue transplant recipients.
- Rapid-onset and severe GVHD, some with fatal outcome, has been reported in patients who had undergone prior allogeneic HSCT and subsequently received PD-1/PD-L1 inhibitors.

CONFIDENTIAL

This document is confidential. Do not disclose or use except as authorized.

Subjects should be screened to determine whether they have undergone a prior allogeneic HSCT prior to participating in nivolumab clinical trials.

- Complications of allogeneic HSCT after treatment with PD-1/PD-L1 inhibitors including nivolumab, administered before allogeneic HSCT, may be associated with an increased risk of transplant-related complications, including GVHD. Fatal cases have been reported in clinical studies. Patients should be monitored closely for early evidence of transplant-related complications

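### On the plain reading, both numeric safety triggers leave out treatment-related deaths from toxicities listed in Section 7.2, and the 13.5 table applies to unexpected events only

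*Combined protocol and SAP*

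**What the plan says.** There are two numeric triggers.

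- **Run-in** (Protocol Summary and Section 1.1): "If three of the ten patients experience a serious, unexpected adverse event during their first cycle of therapy", the study is paused for a safety review. No grade or causal link is required.
- **Section 13.5**: the counted event is "any grade 4 or higher unexpected, adverse event that is assessed as being related to the study intervention". The section tabulates the "probabilities of observing 3 or more SAEs after the 20th patient and before the 40th patient". Its worked example reads "with 20 participants, there is 0.60 probability of observing 3 or more SAEs if a true" rate is 15%.

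The list that bears on expectedness is headed "7.2 Expected Toxicities". It is given drug by drug and includes pneumonitis, hepatitis, encephalitis and Stevens-Johnson syndrome for nivolumab, and sepsis and pulmonary embolism for lenalidomide. Under Section 7.2.1.2 it adds: "Rare cases of myotoxicity (myositis, myocarditis, and rhabdomyolysis), some with fatal outcome, have been reported with nivolumab". The cardiac toxicity table in Section 6.2.7 carries the note "Since this toxicity has caused patient deaths, an aggressive approach is recommended".

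In Section 7.5, a footnote to Table 18 refers to events that the protocol lists as expected, and the grade 5 column covers expected as well as unexpected deaths. The protocol does not define unexpected.

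**The concern.** A run-in and a stopping rule for a new three-drug combination should pick up an excess of severe toxicity, deaths above all. Section 2.7.2 itself notes that combining nivolumab with another drug can make adverse events more common than with one drug by itself. The foreseeable hazard is therefore known toxicities occurring more often or more severely. A count limited to unexpected events is poorly placed to see that.

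If listed means expected, a patient who dies of treatment-related myocarditis adds nothing to either count. The participants have smoldering disease without myeloma-related organ damage, so related deaths are the outcome for which a missing threshold is hardest to defend. A reader of 13.5 may also take the 0.60 as the chance of detecting a 15% rate of all severe related toxicity, which it is not.

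**Working it through.** **Inputs.** Threshold 3, n = 20 and the seven tabulated rates come from 13.5; the run-in threshold of 3 in 10 comes from 1.1. The share of related grade 4 or higher events that count as unexpected, *f*, is not in the documents. It is an assumption, ranged here from 0 to 1.

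**Step 1: reproduce the table.** P(X ≥ 3 | n, p) = 1 − Σ C(n,k) p^k (1−p)^(n−k), summed over k = 0, 1, 2. At n = 20 and p = 0.15 this is 1 − (0.0388 + 0.1368 + 0.2293) = 0.595, against the stated 0.60. For all seven rates:

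| True rate | 1% | 3% | 5% | 10% | 15% | 20% | 30% |
|---|---|---|---|---|---|---|---|
| Stated | 0.001 | 0.021 | 0.075 | 0.32 | 0.60 | 0.79 | 0.96 |
| Computed, n = 20 | 0.0010 | 0.0210 | 0.0755 | 0.3231 | 0.5951 | 0.7939 | 0.9645 |

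The table is exact for 20 patients. It does not fit 39 to 41 patients (at 10%, n = 40 gives 0.78).

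**Step 2: what the table describes.** Its rates are rates of the event defined in 13.5, which must be unexpected. If *p* is the rate of all related grade 4 or higher events, the countable rate is *p* × *f*. At *p* = 15% and *f* = 0.5 it is 0.15 × 0.5 = 0.075; at *f* = 0.25 it is 0.0375. P(3 or more counted in 20):

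| Rate of all related grade ≥4 events | f = 1 | f = 0.5 | f = 0.25 | f = 0.1 | f = 0 |
|---|---|---|---|---|---|
| 10% | 0.32 | 0.08 | 0.01 | 0.001 | 0 |
| 15% | 0.60 | 0.19 | 0.04 | 0.003 | 0 |
| 20% | 0.79 | 0.32 | 0.08 | 0.007 | 0 |
| 30% | 0.96 | 0.60 | 0.19 | 0.02 | 0 |

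**Step 3: run-in.** Here *p* is the rate of serious events in cycle 1, and n = 10. At 20%, P(3 or more) is 0.32 with *f* = 1 and 0.01 with *f* = 0.25. At 30% it is 0.62 and 0.03. With *f* = 0 it is 0 in both cases.

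**Step 4: how a related death from myocarditis is counted.** It is grade 5 and related, so it meets two of the three conditions in 13.5. The third depends on expectedness. The heading of 7.2, the entry in 7.2.1.2 and the Table 18 footnote all point to expected, and the grade 5 column shows that the protocol accepts an expected death. On that reading it adds 0 to both counts.

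**Step 5: effect of counting related deaths.** Taking related-death rates of 2% and 5% as assumptions, P(3 or more deaths) is 0.007 and 0.075 among 20 patients, and 0.001 and 0.012 among 10. If listed related deaths at 2% are added to an unexpected-event rate of 3%, the countable rate is 3% + 2% = 5%, and the chance of reaching three in 20 moves from 0.021 to 0.075.

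**The case against.** A reader might infer that a death from a listed toxicity can never trip a rule, or that nearly all serious toxicities are listed. The documents do not go that far. Unexpected is undefined, and 7.2 gives terms and frequencies, not grades. Section 7.1.2 says that "The following list of reported and/or potential AEs (Section 7.2) and the characteristics of an observed AE (Section 7.3) will determine" whether expedited reporting is needed, so the list is not the only criterion. Fatal outcome is stated for few entries, chiefly muscle and cardiac toxicity and transplant-related events. A sponsor could argue that a fatal form of pneumonitis is unexpected. That stands: exclusion is the plain reading, not a certainty. The same gap means that the count depends on who classifies the death.

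A reader might also infer that the 13.5 table is wrong. It is not: it is exact for the event it defines, and the lower figures in Step 2 rest on an assumed share. What remains is a labelling problem, because the row heading refers only to a true SAE rate.

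Nor are these deaths unmonitored. Table 18 requires grade 5 events to be reported within 24 hours (one business day in the footnote), whether expected or not. The monitoring committee meets regularly, may be given deaths within 30 days of intervention (Section 12.2), and can recommend changes (13.4). This oversight is real, but none of it has a threshold.

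It is tempting to count all listed non-haematologic grade 4 events as well. That would bring in laboratory abnormalities such as raised lipase or transaminases. At an assumed rate of 5% to 10%, such events alone would give a chance of three or more of 0.075 to 0.32 at n = 20 and 0.32 to 0.78 at n = 40. The threshold of three was not tabulated for that event.

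Finally, since September 2017 nivolumab is discontinued and accrual is closed, so the present effect is limited. Both rules nevertheless remain in the January 2018 text, and participants may continue lenalidomide with or without dexamethasone.

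**Conclusion.** The point holds in a limited form. Both numeric triggers carry the unexpected qualifier, and no rule counts related deaths regardless of listing. On the plain reading, a related death from a toxicity named in 7.2 falls outside both counts, and the lack of a definition allows inconsistent counting.

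The size depends on the unlisted share, which the documents do not give. At a 15% rate of all related grade 4 or higher events, the chance of reaching three in 20 patients is anywhere from 0.60, if every event is unlisted, to 0, if none is. The published probabilities should be kept but read as applying to unexpected events in 20 patients. The calculation assumes independent patients, each contributing at most one counted event.

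**What to change.** 1. In 13.5, count every related grade 5 event, whether or not the toxicity appears in 7.2, alongside the unexpected related grade 4 events already counted.
2. In the run-in rule (Protocol Summary and 1.1), add related deaths to the serious, unexpected events already counted. Do not import the grade or causality conditions of 13.5 for the other events, because that would narrow the rule.
3. Define unexpected, and say whether a more severe form of a listed toxicity qualifies.
4. Label the 13.5 table with the event so defined and with n = 20.

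The cost is a change of wording and a slightly higher chance of a safety review, as illustrated in Step 5. The change brings deaths into the count but does not create a separate rule for deaths: one or two alone would still go to the monitoring committee without a threshold. Extending the count to listed non-haematologic grade 4 events is optional, and would need the threshold and the table recalculated first.
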